## 1 INTRODUCTION

This statistical analysis plan (SAP) contains definitions of analysis populations, derived variables and statistical methods for the analysis of the BIOFLOW-V trial. This SAP specifies the pre-planned analyses and serves as the base for the clinical study report.

This SAP is based on the final protocol, version 4.0, dated Feb. 11, 2016.

### 1.1 Trial Objective

The objective of this study is to assess the safety and efficacy of the Orsiro Sirolimus Eluting Coronary Stent System in the treatment of subjects with up to three native *de novo* or restenotic (standard PTCA only) coronary artery lesions compared to the Xience coronary stent system.

### 1.2 Trial Design

BIOFLOW-V is a prospective, multicenter, randomized, controlled trial combining data on the randomized subjects with data from two historical studies by employing a Bayesian approach.

Subjects with coronary artery disease (CAD) that qualify for percutaneous coronary intervention (PCI) with stenting will be screened per the protocol inclusion and exclusion criteria to achieve a total of at least 1,334 and up to 1,400 randomized subjects. Eligible subjects will be randomized, stratified by study center, in a 2:1 ratio to undergo percutaneous coronary revascularization with either the Orsiro Sirolimus Eluting Stent System (treatment group, at least 889 and up to 933 subjects) or the Xience Everolimus Eluting Stent System (control group, at least 445 and up to 467 subjects). The study will include up to 100 clinical sites in the United States and 50 clinical sites outside of the United States.

BIOFLOW-V randomized subjects will be combined with historical Orsiro, Xience Prime™ and Xience Xpedition™ randomized subjects from the BIOFLOW-II and BIOFLOW-IV trials by employing a Bayesian statistical approach. Only subjects that meet all clinical and angiographic eligibility criteria of the BIOFLOW-V trial will be included in the analysis.

### 1.3 Primary Endpoint

The primary endpoint of the study is Target Lesion Failure (TLF) rate at 12 months post-index procedure. TLF is defined as all cardiac death, protocol-defined target vessel Q-wave or non-Q-wave myocardial infarction (MI), or clinically driven target lesion revascularization (TLR).

The TLF rate will be derived from events adjudicated by the CEC to be a cardiac death, protocol-defined Q-wave or non-Q-wave target vessel myocardial infarction, or a clinically-driven target lesion revascularization according to the CEC manual of operations and definitions.

### 1.4 Secondary Endpoints

The secondary endpoints include the following measures:

- 1) Device success, defined as attainment of < 30% residual stenosis of the target lesion using the assigned study stent only. *Note: Post-dilation is allowed to achieve device success.*
- 2) Lesion success, defined as attainment of < 30% residual stenosis of the target lesion using any percutaneous method.

- 3) Procedure success, defined as attainment of < 30% residual stenosis of the target lesion using the assigned study stent only without occurrence of in-hospital major adverse cardiac events (MACE; composite of all-cause death, protocol-defined Q-wave or non-Q-wave MI, and any clinically-driven TLR).

The percent residual stenosis, as assessed by the investigator visual estimate or on-line QCA during the procedure, will be used as the primary analysis measure of the final % diameter stenosis for evaluating angiographic success criteria for these endpoints. If investigator assessment of residual stenosis is not available, the final % diameter stenosis as assessed by QCA will be used. In evaluating procedure success, MACE will be based on CEC adjudicated event data.

The following secondary clinical endpoints will be evaluated prior to discharge, at 1, 6 and 12 months and annually thereafter through 5 years follow-up:

- 4) Death
- 5) Protocol-defined MI
- 6) Cardiac death or protocol-defined MI
- 7) MACE and individual MACE components (all-cause death, protocol-defined Q-wave or non-Q-wave MI, and any clinically-driven TLR)
- 8) TLF and individual TLF components (cardiac death, protocol-defined target vessel Q-wave or non-Q-wave MI, and any clinically-driven TLR)
- 9) Target vessel failure (TVF) and individual TVF components (cardiac death, protocol-defined target vessel Q-wave or non-Q-wave MI, and any clinically-driven TVR)
- 10) Stent thrombosis (all, definite, definite/probable, probable, possible) according to Academic Research Consortium (ARC) criteria for acute, subacute, late, very late and cumulative stent thrombosis

Analysis of secondary endpoints will be based on CEC adjudicated event data

## 2 PLANNED ANALYSES

### 2.1 General Analysis Definitions

Bayesian analyses will be performed using the open-source program OpenBUGS version 3.2.3 (Bayesian inference using Gibbs Sampling), Lunn et al.; other analyses, including summaries, will be conducted using SAS (version 9.4), unless otherwise noted. Descriptive statistics for continuous variables will include mean, standard deviation, median, quartiles, minimum, maximum, and sample size for each treatment group. Categorical variables will be summarized using counts and percentages. Proportions will be calculated using known non-missing values. Unless otherwise indicated, all statistical tests and/or confidence intervals will be performed at  $\alpha = 0.05$  (2-sided).

---

## 2.2 Prior Data

The Orsiro clinical trial program includes BIOFLOW-II, BIOFLOW-IV and BIOSCIENCE, three randomized controlled trials in which subjects were randomized to the Orsiro stent against the Xience Prime™ or Xience Xpedition™ stents. A brief description of these trials is provided in protocol Section 3.5. The inclusion and exclusion criteria for BIOFLOW-II and BIOFLOW-IV are nearly identical to those proposed for BIOFLOW-V, whereas the inclusion and exclusion criteria in BIOSCIENCE were more liberal to allow enrollment of a broadly inclusive real world population. The primary non-inferiority analysis of the BIOFLOW-V study will use data from the BIOFLOW-II and BIOFLOW-IV trials prospectively using a Bayesian approach. Data from the BIOSCIENCE trial will not be included for analysis due to the more liberal enrollment criteria. A summary of the comparison of the study design of BIOFLOW-II and BIOFLOW-IV trials along with the proposed BIOFLOW-V study was listed below.

	BIOFLOW -II	BIOFLOW-IV	BIOFLOW-V
Eligibility Criteria	All subjects will match BIOFLOW-V clinical and angiographic inclusion/exclusion criteria		
Primary or Secondary Endpoint Definition	TLF: cardiac death, target vessel Q-wave or non-Q wave MI, CABG, clinically driven TLR		
Follow-up schedule	1mo, 6mo, 9mo angio, 12mo, 2yr, 3yr, 4yr, 5yr	1mo, 6mo, 12mo, 2yr, 3yr, 4yr, 5yr	1mo, 6mo, 12mo, 2yr, 3yr, 4yr, 5yr
Enzyme measurements	CK, CKMB (optional) and Troponin: 
 
• Baseline
 
• Within 6-24 hours after the index procedure or at discharge, whichever comes first
 
	CK, CKMB (optional) or Troponin (if CK and CKMB are not used): 
 
• Baseline
 
• Within 6-24 hours after the index procedure or at discharge, whichever comes first
 
	CK, CKMB, Troponin (if CKMB is not available): 
 
• Baseline
 
• Within 6-24 hours after the index procedure
 

Clinical Monitoring	
 
• 100% source verification
 
• Independent core labs for angiography, IVUS & OCT
 
• On-site monitoring
 
• Independent CEC adjudication
 
	
 
• 100% source verification
 
• Independent angiographic core lab
 
• On-site Monitoring
 
• Independent CEC adjudication
 
	
 
• 100% source verification
 
• Independent angiographic core lab
 
• On-site Monitoring
 
• Independent CEC adjudication
 

To ensure the validity of data from subjects across trials, the following measures will be taken:

- Evaluation of the 12-month TLF rate (a primary endpoint in the BIOFLOW-V and a secondary endpoint in the BIOFLOW-II and IV trials) will be performed in a uniform fashion, using a consistent set of definitions and similar follow-up schedule:
  - The measurement schedule of cardiac enzymes is similar in all trials: cardiac enzymes are collected once within 6-24 hours post index procedure. While all trials mandated collection of CK and CKMB, the BIOFLOW-II also mandated measurement of troponin. The BIOFLOW-IV and BIOFLOW-V trials allow measurement of troponin if CK and CKMB are not used. To address the differences in the collection of

- cardiac enzymes between the three trials, a uniform definition of peri-procedural MI that is based on CK and CKMB levels (with troponin levels used only in the absence of CK and CKMB) will be utilized.
- All trials have similar clinical follow-up schedule at 1 month (telephone contact/clinic visit), 6 months (telephone contact/clinic visit) and 12 months (telephone contact/clinic visit for BIOFLOW-II clinic visit for BIOFLOW-IV and BIOFLOW-V).
  - The BIOFLOW-II and BIOFLOW-IV trials used the same independent angiographic core laboratory. To ensure consistency, angiograms from the BIOFLOW-II, BIOFLOW-IV and BIOFLOW-V trials will be analyzed or validated by the same angiographic core laboratory.
  - All clinical endpoints (potential TLR, MI and death events) will be re-adjudicated by the same independent CEC as will be employed for the BIOFLOW-V data, using uniform definitions.
- Data quality will be confirmed in accordance with the monitoring plan of each trial.
  - Only subjects that meet all BIOFLOW-V clinical and angiographic eligibility criteria will be included. The criteria include the following:

### Clinical Inclusion Criteria

Subjects must meet all of the following criteria to participate in the trial:

- 1) Subject is  $\geq 18$  years or the minimum age required for legal adult consent in the country of enrollment.
- 2) Subject is an acceptable candidate for PCI.
- 3) Subject is an acceptable candidate for CABG.
- 4) Subject has clinical evidence of ischemic heart disease, stable or unstable angina pectoris or documented silent ischemia.
- 5) Subject is eligible for dual anti-platelet therapy treatment with aspirin plus either clopidogrel, prasugrel, ticagrelor or ticlopidine.
- 6) Subject has provided written informed consent.
- 7) Subject is willing to comply with study follow-up requirements.

### Angiographic Inclusion Criteria

Each target lesion/vessel must meet all of the following angiographic criteria for the subject to be eligible for the trial:

- 1) Subject has up to three target lesions in up to two separate target vessels (two target lesions in one vessel and one target lesion in a separate vessel).
- 2) Target lesion must be de novo or restenotic lesion in native coronary artery; restenotic lesion must have been treated with a standard PTCA only.
- 3) Target lesion must be in major coronary artery or branch (target vessel).
- 4) Target lesion must have angiographic evidence of  $\geq 50\%$  and  $< 100\%$  stenosis (by operator visual estimate). If the target lesion is  $< 70\%$  stenosed, there should be clinical evidence of ischemia such as a positive functional study (e.g. exercise treadmill test, thallium stress test, SPECT, or stress echo), cardiac computed tomography (CT), electrocardiography, fractional flow reserve, or post infarct angina.
- 5) Target vessel must have a Thrombolysis In Myocardial Infarction (TIMI) flow  $> 1$ .
- 6) Target lesion must be  $\leq 36$  mm in length by operator visual estimate.
- 7) Target vessel must have a reference vessel diameter of 2.25–4.0 mm by operator visual estimate.
- 8) Target lesion must be amenable to treatment with a maximum of two overlapping stents.

**Clinical Exclusion Criteria**

Subjects will be excluded from the trial if any of the following criteria are met:

- 1) Subject has clinical symptoms and/or ECG changes consistent with acute ST elevation MI (STEMI) within 72 hours prior to the index procedure.
  - Note: Hemodynamically stable non-STEMI (NSTEMI) subjects are eligible for study enrollment
- 2) Subject is hemodynamically unstable.
- 3) Subject is pregnant and/or breastfeeding or intends to become pregnant during the duration of the study.
- 4) Subject has a known allergy to contrast medium that cannot be adequately pre-medicated, or any known allergy to thienopyridine, aspirin, both heparin and bivalirudin, L-605 cobalt-chromium (Co-Cr) alloy or one of its major elements (cobalt, chromium, tungsten and nickel), acrylic, fluoropolymers, silicon carbide, PLLA, sirolimus or everolimus.
- 5) Revascularization of any target vessel within 9 months prior to the index procedure or previous PCI of any non-target vessel within 30 days prior to the index procedure.
- 6) Planned treatment of a lesion not meeting angiographic inclusion and exclusion criteria during the index procedure or after the index procedure.
- 7) Planned surgery within 6 months of index procedure unless dual antiplatelet therapy can be maintained throughout the peri-surgical period.
- 8) History of a stroke or transient ischemic attack (TIA) within 6 months prior to the index procedure.
- 9) Subjects with active bleeding disorders, active coagulopathy, or any other reason, who are ineligible for DAPT.
- 10) Subject will refuse blood transfusions.
- 11) Subject has documented left ventricular ejection fraction (LVEF) < 30% as evaluated by angiography, echocardiogram, radionuclide ventriculography or any non-invasive imaging method within 90 days prior to the index procedure.
- 12) Subject is dialysis-dependent.
- 13) Subject has impaired renal function (i.e., blood creatinine > 2.5 mg/dL or 221 µmol/L determined within 7 days prior to the index procedure).
- 14) Subject has leukopenia (i.e. < 3,000 white blood cells/mm^3), thrombocytopenia (i.e. < 100,000 platelets/mm^3) or thrombocytosis (i.e. > 700,000 platelet/mm^3).
- 15) Subject is receiving oral or intravenous immunosuppressive therapy (inhaled steroids are permitted), or has known life-limiting immunosuppressive or autoimmune disease (e.g., human immunodeficiency virus, systemic lupus erythematosus; diabetes mellitus is permitted).
- 16) Subject is receiving chronic anticoagulation (e.g. coumadin, dabigatran, apixaban, rivaroxaban or any other agent).
- 17) Subject has life expectancy of < 1 year.
- 18) Subject is participating in another investigational (medical device or drug) clinical study. Subjects may be concurrently enrolled in a post-market study, as long as the post-market study device, drug or protocol does not interfere with the investigational treatment or protocol of this study.
- 19) In the investigator's opinion, subject will not be able to comply with the follow-up requirements.

**Angiographic Exclusion Criteria**

Subjects will be excluded from the trial if any of the target lesions/vessels meets any of the following angiographic criteria:

- 1) Target lesion is located within a saphenous vein graft or arterial graft.

- 2) Target lesion is a restenotic lesion that was previously treated with a bare metal or drug eluting stent (in-stent restenosis).
- 3) Target lesion has any of the following characteristics:
  - a. Lesion location is within the left main coronary artery, or within 3 mm of the origin of the left anterior descending (LAD) or left circumflex (LCX).
  - b. Involves a side branch of > 2.0 mm in diameter.
    - Note: Lesions within 3 mm of the origin of the right coronary artery may be treated.
- 4) Target vessel/lesion is excessively tortuous/angulated or is severely calcified, that would prevent complete inflation of an angioplasty balloon. This assessment should be based on visual estimation.
- 5) Target vessel has angiographic evidence of thrombus.
- 6) Target lesion is totally occluded (100% stenosis).
- 7) Target vessel was treated with brachytherapy any time prior to the index procedure.

### 2.3 Bayesian Analysis

To assess the non-inferiority of the Orsiro stent compared to the Xience stent in the BIOFLOW-V study, a Bayesian approach using hierarchical models to formally incorporate data from the BIOFLOW-II and BIOFLOW-IV trials will be employed. The approach proposes using Binomial analysis for the presence of a TLF event and a Bayesian model that allows for a bias between the TLF event rates of the BIOFLOW-II and BIOFLOW-IV trials and the TLF event rates of the BIOFLOW-V trial in both the Orsiro and Xience groups. The parameters defining the bias are selected so that the proposed method is robust to misspecifications of the initial assumptions.

Whenever not specified, priors in Bayesian analyses will be non-informative or weakly informative priors. The following priors will be employed unless otherwise specified: normal priors with mean 0 and large variance for slope parameters, inverse gamma priors with parameter 0.001 and 0.001 and Beta (1,1) for probability parameters.

### 2.4 Criteria for Success

The criterion for success is based on the posterior probability of the alternative hypothesis (i.e., of non-inferiority being met). The Orsiro group will be declared non-inferior to the Xience group if the posterior probability of the alternative hypothesis  $H_A$  is large, that is

$$P(H_A|Data) = P(\pi_X^V - \pi_O^V > -\delta | Data) > \pi^*$$

where  $\pi_X^V$  and  $\pi_O^V$  are the 1-year TLF for the Xience and Orsiro groups of the BIOFLOW-V study, respectively,  $\delta$  is the non-inferiority margin and  $H_A: \pi_X^V - \pi_O^V > -\delta$  is the alternative hypothesis indicating that non-inferiority is met and  $\pi^* = 0.975$  is the level of evidence we require to declare the alternative hypothesis true.

### 2.5 Sample Size Determination

The BIOFLOW-V trial will assess non-inferiority of the 12-month TLF rate for the Orsiro stent vs. TLF rate in subjects treated with the Xience stent. The null hypothesis  $H_0$  is that the Orsiro stent will have a primary endpoint (TLF) rate equal to or exceeding that of the Xience group by the non-inferiority margin or more. The alternative hypothesis  $H_A$  is that the Orsiro stent will have TLF rate less than the Xience group rate plus the non-inferiority margin. Specifically:

$$\begin{aligned} H_0: \pi_X^V - \pi_O^V &\leq -\delta \\ H_A: \pi_X^V - \pi_O^V &> -\delta \end{aligned}$$

Where  $\pi_O^V$  is the true 12-month TLF rate for the Orsiro stent,  $\pi_X^V$  is the true 12-month TLF rate for the Xience arm, and  $\delta$  is the non-inferiority margin.

The assumptions for this analysis are:

- True 12-month TLF rate is 7.0% in both treatment groups ( $\pi_X^V = \pi_O^V$ ).
- Power is 89%.
- 3.85% is the absolute non-inferiority margin (55% relative non-inferiority margin).
- Discount the results of the BIOFLOW-IV data by 20% and BIOFLOW-II data by 30%.
- Standard deviation of the bias terms between the odds of BIOFLOW-II TLF 12-month rates and odds of BIOFLOW-V 12-month rates is 0.3.
- Standard deviation of the bias terms between the odds of BIOFLOW-IV TLF 12-month rates and odds of BIOFLOW-V 12-month rates is 0.3.
- Non-inferiority assessment will be assessed using the posterior probability of the alternative hypothesis as specified above, where  $\pi^* = 0.975$

Rejection of the null hypothesis signifies that the Orsiro stent is not inferior to the Xience stent with regards to 12-month TLF. A total of 1,200 subjects (800 in the Orsiro group and 400 in the Xience group) will have 89.6% power to reject the above null hypothesis in favor of the alternative under the stated assumptions. To account for loss to follow-up (expected to be approximately 10%), a total of 1,334 subjects will need to be randomized. The one-sided type I error estimates are 4.0%, 3.3%, and 4.2% if the actual odds for the 12-month TLF rate of event in the Xience group of the BIOFLOW-IV study are the same, 10% lower and 10% higher when compared with the odds for the 12-month TLF rate of event in the Xience group of the BIOFLOW-V study.

### 2.5.1 True Rate

The current assumption of the 12-month TLF rate of 7.0% is based on expected inclusion criteria for BIOFLOW studies and results from recent everolimus eluting stent trials.

### 2.5.2 Non-Inferiority Margin

The non-inferiority margin was calculated based on a meta-analysis rate of the difference in treatment effect between DES and BMS. Randomized clinical trials comparing treatment with DES and treatment with BMS with 9 months or longer clinical follow-up data were included in the meta-analysis. Nine-month rates were used whenever 12-month rates were not available. Depending on study definitions, TVF or MACE rates were used to match as closely as possible the TLF definition in this study.

The meta-analytic rate of the difference in treatment effect between DES and BMS was 10.0% with a lower bound of the 2-sided 95% CI of 8.2%. A common practice is to take 50% of this lower bound of the DES-BMS difference as the non-inferiority margin, therefore an absolute non-inferiority margin of 3.85%, which is approximately 46% of the lower bound, is supported.

## 2.6 Statistical Analysis Sets

### 2.6.1 Intention to Treat (ITT) Analysis Population

The Intent-to-Treat (ITT) population is defined as all randomized subjects. Subjects are analyzed according to the stent to which they were randomized (regardless of the actual stent that they received). This is the primary analysis population.

### 2.6.2 Per-Protocol (PP) Analysis Population

The Per-Protocol (PP) population is defined as all randomized subjects who received at least one assigned study stent, have sufficient follow-up data (at least 330 days of follow-up or experienced the primary endpoint) and no major protocol eligibility violations (i.e. inclusion/exclusion criteria violations that could impact the primary endpoint).

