7.4.5. Bailout Procedures

In the event of a major dissection or an occlusive complication manifested as decreased target vessel flow, chest pain or ischemic ECG changes after index procedure that do not respond to repeat balloon inflations or intracoronary vasodilators (nitroglycerin, verapamil, diltiazem, nitroprusside), other bailout procedures may be performed, which may include additional stenting. Should an additional stent be used, it must be the assigned study stent unless clinically contraindicated. Multiple stenting with the Orsiro or Xience stents requires a 2-mm overlap. Such procedures must be documented in the eCRF.

All bailout procedures are considered adverse events (AEs) in this study. Bailouts procedures that result in any of the consequences characteristic of a serious adverse event (SAE) (e.g. death, prolonged hospitalization, etc. see Section 9.1.3) are considered SAEs.

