7.4.6. Bailout-Staged Procedure

Planned staged procedures are not allowed in this clinical investigation. If during the intervention it becomes clinically necessary to postpone treatment of the second and/or third lesion to a later time point, this is regarded as a staged procedure and must be documented as such. For staged procedures, the use of an investigational stent is not allowed. Subjects requiring staged procedure should be treated according to the investigator's discretion and standard of care. These subjects should receive an approved, commercially available treatment and not a study stent.

All bailout procedures are considered adverse events (AEs) in this study.

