8.6.2. Per-Protocol Population

The Per-Protocol (PP) population is defined as all randomized subjects who received at least one assigned study stent, have sufficient follow-up data (at least 11 months of follow-up or experienced the primary endpoint) and no major protocol eligibility violations (i.e. inclusion/exclusion criteria violations that could impact the primary endpoint).

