### 2.6.3 Modified Intent-to-Treat Analysis Population

The Modified ITT population is defined as all randomized subjects who received at least one study stent according to their treatment assignment.

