## 2.7 Analysis of Primary Endpoint

This study will assess non-inferiority of the 12-month TLF rate for the Orsiro stent vs. the Xience stent. The analysis will be carried out on the ITT set (primary), modified ITT and PP analysis sets. The null hypothesis  $H_0$  is that the Orsiro stent will have a primary endpoint (12-month TLF) rate equal to or exceeding that of the Xience group by the non-inferiority margin or more. The alternative hypothesis  $H_A$  is that the Orsiro stent will have a 12-month TLF rate less than the Xience group rate plus the non-inferiority margin. The hypothesis is defined as follows:

$$\begin{aligned} H_0: \pi_X^V - \pi_O^V &\leq -\delta \\ H_A: \pi_X^V - \pi_O^V &> -\delta \end{aligned}$$

where  $\pi_O^V$  is the true 12-month TLF rate for the Orsiro stent,  $\pi_X^V$  is the true 12-month TLF rate for the Xience arm, and  $\delta$  is the non-inferiority margin chosen to be 0.0385 (or 3.85%) as noted in section 2.5.2, Non-Inferiority Margin.

The proposed model is a Bayesian hierarchical model that assumes a bias between the 12-month TLF rates in BIOFLOW-II and BIOFLOW-V as well as BIOFLOW-IV and BIOFLOW-V studies.

Estimation of the parameters and hypotheses testing of the primary hypotheses is based on the posterior distribution of the parameters. The posterior distribution for parameters which do not have closed form posterior inferences will be carried out by sampling from the posterior distribution of the parameters. The freely available program OpenBUGS (Bayesian inference using Gibbs Sampling) will be used to obtain samples from the posterior distribution of the parameters. Using OpenBUGS, 100,000 samples will be obtained from the posterior distribution of 12-month TLF rates after the initial 5,000 will be discarded. To decrease autocorrelation, only every tenth sample will be used in calculations.

We will check convergence of the MCMC sampler using the Brooks-Gelman-Rubin method. Convergence of the sampler will be established if the ratio of within-chain and between-chain variability for multiple chains starting at different initial values will be close to 1.

The percent of posterior samples that satisfy  $\pi_X^V - \pi_O^V > -\delta$  will be used to estimate the posterior probability of the alternative hypothesis will be calculated and reported in the table below.

Table reporting the posterior probability of the Alternative Hypothesis:

Alternative Hypothesis	Posterior Probability

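### The per-protocol set admits subjects with a non-assigned stent in another target lesion, so no planned analysis limits the primary endpoint to subjects treated only as assigned

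*SAP*

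**What the plan says.** SAP 2.6.2 puts three conditions on PP:

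- Stent: "all randomized subjects who received at least one assigned study stent". Protocol 8.6.2 has the same rule.
- Follow-up: "at least 330 days of follow-up or experienced the primary endpoint".
- Violations: "no major protocol eligibility violations (i.e. inclusion/exclusion criteria violations that could impact the primary endpoint". This covers eligibility only, not treatment deviations.

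SAP 2.6.3 defines mITT as "all randomized subjects who received at least one study stent according to their treatment assignment". On the use of the sets, SAP 2.7 states: "The analysis will be carried out on the ITT set (primary), modified ITT and PP analysis sets".

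The protocol allows up to three target lesions in two vessels, with at most two study stents per lesion (sections 5 and 7.4.3). It limits mixed treatment. All target lesions are to get the assigned stent (7.4.3), crossover is not permitted (7.4.1, Randomization), and planned staging is not allowed (7.4.6).

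It also leaves routes to mixed treatment. On an additional bailout stent, 7.4.5 says "it must be the assigned study stent unless clinically contraindicated". On subjects whose second or third lesion is deferred, 7.4.6 says "These subjects should receive an approved, commercially available treatment and not a study stent". Section 7.4.1 (Randomization) foresees subjects who receive a stent other than the one assigned.

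**The concern.** In a non-inferiority trial, crossover to the comparator pulls the arms together in ITT and so favours a positive result. PP is normally the analysis that shows whether this mattered. Here a subject randomized to Orsiro, with Orsiro in one lesion and Xience in another against the protocol, is a PP Orsiro subject if follow-up and eligibility are in order. A failure at the Xience-treated lesion counts as an Orsiro failure, and the reverse holds in the Xience arm.

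Because mITT has the same stent rule, it does not help. What is at stake is the reassurance drawn from three concordant analyses, not the primary test.

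**Working it through.** **Step 1. Compare the sets.** Strategy 1 in SAP 2.8 already requires 330 days of follow-up or an event in every set.

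| Set | Assigned-stent rule | Rule on other stents | Eligibility violations |
|---|---|---|---|
| ITT | none | none | kept |
| mITT | at least one | none | kept |
| PP | at least one | none | major ones excluded |

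Under strategy 1, PP and mITT differ only by eligibility violations. No set removes a subject because of a non-assigned stent in a second or third lesion.

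**Step 2. Reproduce the plan's figures (SAP 2.5).**

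- Randomized number: 1,200 / 0.90 = 1,333.3, so 1,334. With the increase in protocol 8.5, 1,260 / 0.90 = 1,400. Both agree with the plan.
- Power: the borrowing model was simulated with 10,000 trials of 400 Xience and 800 Orsiro subjects. It used binomial likelihoods and a flat prior. BIOFLOW-IV was weighted 0.8 and BIOFLOW-II 0.7, with bias SD 0.3 on the log-odds and success if the posterior probability exceeds 0.975.
- BIOFLOW-II was fixed at 12/148 Xience and 19/287 Orsiro. These counts are rounded from the 8.0% and 6.5% in protocol 3.5 and the completers in 8.1. BIOFLOW-IV was simulated with 185 and 370 subjects.
- Power came to 88.9% against the stated 89.6%. Drawing all historical rates at 7% gave 85.4%.
- Type I error came to 3.9%, 3.7% and 4.2% against the stated 4.0%, 3.3% and 4.2%. The Monte Carlo standard error is about 0.2 points.

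The model is close enough to the plan's to measure the effect of mixing.

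**Step 3. Add mixed treatment.** The documents give no frequency, so a range is assumed. Let m be the share of subjects who are mixed. Let w be the share of a mixed subject's risk that moves to the other arm's level. The true rates are 7.0% for Xience and 7.0 + 3.85 = 10.85% for Orsiro, so the true difference is at the margin.

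- Both arms mixed: difference shown = 3.85 × (1 − 2wm)
- Orsiro only: difference shown = 3.85 × (1 − wm)

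For example, with w = 0.5, m = 5% and both arms mixed, 3.85 × (1 − 0.05) = 3.66 points. Results for w = 0.5:

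| m | Difference, both arms | False non-inferiority, both arms | Difference, Orsiro only | False non-inferiority, Orsiro only |
|---|---|---|---|---|
| 0% | 3.85 | 3.9% | 3.85 | 3.9% |
| 1% | 3.81 | 4.3% | 3.83 | 4.1% |
| 2% | 3.77 | 4.4% | 3.81 | 4.1% |
| 5% | 3.66 | 4.7% | 3.75 | 4.6% |
| 10% | 3.47 | 6.3% | 3.66 | 4.8% |
| 20% | 3.08 | 9.6% | 3.47 | 6.3% |

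The increases at 1–2% are close to simulation noise. A shorter run of 4,000 trials gave 5.2% at m = 5% and 6.9% at m = 10% with both arms mixed, so the figures are approximate. With m = 5% in both arms, w = 0.33 gives 3.85 × (1 − 0.033) = 3.72 points, and w = 0.67 gives 3.85 × (1 − 0.067) = 3.59.

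**Step 4. Cost of removing mixed subjects.** Simulated power is 89.3% with 2% removed, 87.9% with 5% and 87.8% with 10% (standard error about 0.3 points).

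**The case against.** **Mixing should be rare.** The protocol forbids crossover and planned staging, and additional stents for dissection follow the original assignment. This stands. A reader might infer that PP is in fact diluted, but the documents give no frequency and so support only that it could be.

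**The direction is not certain.** A deferred lesion is to receive something other than a study stent, and protocol 7.7 uses that term for both Orsiro and Xience. On that wording the device is not the comparator. If it does worse than Orsiro, charging its failures to Orsiro works against non-inferiority. TLF is also a subject-level composite with cardiac death and target-vessel MI, so a per-lesion scaling is only approximate. Both points stand. Step 3 applies to mixing with the comparator or a device that performs like it.

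**Excluding every mixed subject could be worse.** A reader might infer that PP should drop all of them. Bailout follows a major dissection or occlusive complication, and staging follows clinical necessity during the intervention. Either may be a consequence of the assigned device and may bring a peri-procedural MI, which is a TLF component. Dropping these subjects could flatter the worse device. It would also remove subjects who followed 7.4.5 or 7.4.6 from a set called per-protocol. This stands and shapes the fix.

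**Part of the signal is already reported.** Device success requires the assigned stent only, while lesion success allows any percutaneous method. Both are reported by arm (SAP 1.4 and 2.9). The gap between them hints at non-assigned device use, but it does not give the primary endpoint in subjects treated as assigned.

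**Borrowed subjects.** SAP 2.6.4 sets no treatment-received condition for BIOFLOW-II and BIOFLOW-IV subjects, so a stricter BIOFLOW-V set leaves the borrowed data as they are. This limits what the fix can show.

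**Conclusion.** The gap in the definition is certain: neither PP nor mITT excludes a subject for a non-assigned stent in another target lesion, and no other clause does so. Concordance of ITT, mITT and PP is therefore weak evidence that mixed treatment did not matter.

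The effect is of unknown and probably small size. With 2–5% of subjects mixed, false non-inferiority in PP goes from about 3.9% to about 4.1–4.7%. This assumes a true difference at the margin, half of a mixed subject's risk moved to the other arm's level, and 400 and 800 subjects analysed. It becomes material only if mixing is common: at 10% it is about 4.8–6.3%.

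A reader might infer that the non-inferiority conclusion is compromised. The documents do not support that. The decision rests on ITT, which is defined by randomization and is unaffected, and no stated figure is wrong because of this point. It concerns how informative a supportive analysis is.

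**What to change.** 1. In SAP 2.6.2 and protocol 8.6.2, exclude from PP subjects who received a non-assigned stent in a target lesion at the index procedure in breach of the protocol (crossover). Keep index bailout subjects (7.4.5) and staged subjects (7.4.6) in PP.
2. In SAP 2.7, add one supportive primary-endpoint analysis limited to subjects whose target lesions received only the assigned stent. Bailout subjects given a non-assigned stent and staged subjects are removed only here.
3. Report by arm the number of subjects with a non-assigned stent, split into crossover, bailout and staged, with their TLF events. Any removal of device-related complications is then visible.
4. State whether a deferred lesion still counts as a target lesion for TLF and for these sets. The documents leave this open: 7.4.6 does not say, and Appendix B defines the target lesion, under its TLR entry, by the stented segment.
5. Leave ITT and mITT unchanged.

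The cost is wording, one extra supportive run, slightly fewer PP subjects, and post-randomization selection in the supportive set. The documents do not list the eCRF fields, so the sponsor should confirm that stent identity is recorded per lesion. Device success cannot be derived without knowing whether only the assigned stent was used, and the protocol requires bailout and staged procedures to be documented, so the information is probably available.
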